8.6.1.2. Type 1B Endoleaks

A potential treatment option for Type 1B endoleaks have been identified, which can be used based on the physician's preference:

- Distal Covered Stents

The table below summarizes this options, aligning each with evaluation criteria:

Implant and Anatomic Evaluation Criteria	Potential Treatment Options for Type IB Endoleaks
Inadequate sealing in the between the Nellix Endobags and the iliac vessel wall	
- Distal Covered Stent Extenders (Ovation iX Iliac Stent Graft)

8.6.2. Treatment Options for Migration

The recommendation for treatment of migration is based on evaluation of the distance the implant has migrated, presence of endoleak and comparison between proximal and distal migration distances. Based on evaluation of these factors, three potential treatment options for the treatment of migration have been identified:

- CT Surveillance
- Nellix proximal extenders with or without commercially available stent grafts in the visceral arteries (NiNA with polymer/ Secondary ChEVAS)
- Nellix Stent Relining (NiNA without Polymer)
 - For subjects in which the proximal migration is more significant than the distal migration of the Nellix implant, stent relining should prevent or slow the rate of migration. Relining the stent will increase the stiffness and column strength of the Nellix implant which may increase its resistance to the hemodynamic forces acting upon it.

The table below summarizes these options, aligning each with evaluation criteria:

Implant and Anatomic Evaluation Criteria	Potential Treatment Options for Migration
Nellix implant has migrated <10mm, in the absence of Type 1A endoleak and a proximal seal zone of at least 10mm remains	- CT Surveillance (Enhanced Follow-up)
Nellix implant has migrated ≥ 10 mm, in the absence of Type 1A endoleak and a proximal seal zone of at least 10mm remains	- Nellix Relining (NiNA without Polymer)
Implant migration associated with Type 1A endoleak and a proximal neck of at least 30mm is available	- Nellix Proximal Extenders (NiNA with Polymer)
Implant migration associated with Type 1A endoleak and a proximal neck of less than 30mm is available	- Nellix Proximal Extenders with commercially available stent grafts (iCAST) in the visceral arteries (Secondary ChEVAS)

8.6.3. Treatment Options for Aneurysm Expansion

The recommendation for treatment of aneurysm expansion is based on the presence of Type 1A/B endoleaks. Based on evaluation of these factors, two potential treatment options for the treatment of aneurysm expansion have been identified:

- Type 1A Endoleak Treatments
- Distal Extension (Ovation iX Iliac Stent Graft)

The table below summarizes these options, aligning each with evaluation criteria:

Implant and Anatomic Evaluation Criteria	Potential Treatment Options for Aneurysm Expansion
Aneurysm expansion is associated with Type 1A endoleak	Refer to treatment option for Type 1A endoleak for further detail
Aneurysm expansion is associated with Type 1B endoleak	- Distal Covered Stent Extenders (Ovation iX Iliac Stent Graft)
Aneurysm expansion in the absence of endoleak	- Distal Covered Stent Extenders (Ovation iX Iliac Stent Graft)

8.7. PROTOCOL DEVIATIONS

A protocol deviation occurs when a clinical investigator and/or study site personnel do not conduct the study according to the clinical investigational plan. All deviations are recorded on a Protocol Deviation Form. United States regulations (21 CFR 812.140) require that investigators maintain accurate, complete, and current records relating to the clinical study. This includes documents showing the dates and reasons for each deviation from the clinical investigational plan. Depending upon the nature of the protocol deviation, expedited reporting and prior approval from Endologix may be required. All deviations will be summarized and submitted in IDE progress reports, annual reports, and the final study report to FDA.

If Endologix finds that an investigator is not complying with the executed study agreements, the investigational plan, FDA regulations, or the requirements of the reviewing IRB, prompt action will be taken to secure compliance. In addition, shipment of the device may be stopped or the participation of the investigator may be terminated.

8.7.1. Deviations with Expedited Reporting Requirements

For the following types of protocol deviations (per 21 CFR 812.150), an investigator is required to notify Endologix and the IRB within 5 business days of the deviation.

- Emergency Deviation from the Investigational Plan (a deviation to protect the life or physical well-being of a subject in an emergency).
- Failure to obtain Informed Consent

Notification to Endologix and/or the IRB should be documented and maintained in the clinical study file at the site and at Endologix.

8.7.2. Deviations Requiring Prior Approval

An investigator is required to obtain prior approval from clinical study management at Endologix and the IRB before initiating deviations from the Investigational Plan that affect the scientific soundness of the plan, or the rights, safety, and welfare of the subjects (non-emergent situation). However, prior approval is not required in situations where unforeseen circumstances are beyond the investigator's control, e.g., subject did not attend scheduled follow-up visit, laboratory test was performed incorrectly, and test equipment did not operate properly.

8.7.3. Non-Urgent Deviations

Protocol deviations which do not have the urgency associated with expedited notification or prior Endologix/ IRB approval (as discussed in the above paragraphs)

will be reported upon discovery, such as during completion of eCRFs or a monitoring visit.

8.8. ADVERSE EVENT REPORTING

Adverse events will be entered on the applicable eCRF and in the patient's medical records. The date of onset, severity, and action taken are requested to be identified by the PI.

8.8.1. General Definitions

An adverse event (AE) is any undesirable clinical occurrence in a patient enrolled in the trial that does not necessarily have a causal relationship with the treatment. An AE can therefore be any unintended sign, symptom or disease temporally associated with the use of an investigational product, whether or not related to the use of the product.

A serious adverse event (SAE) is an adverse event that:

- Led to a death.
- Led to a serious deterioration in the health of the subject that:
 - a. Resulted in life threatening illness or injury.
 - b. Resulted in a permanent impairment of a body structure or a body function.
 - c. Required in-patient hospitalization or prolongation of existing hospitalization.
- Resulted in medical or surgical endovascular procedure to prevent permanent impairment to a body structure or a body function.
- Led to fetal distress, fetal death, or a congenital abnormality or birth defect.

An unanticipated adverse device effect (UADE) is any serious adverse effect on health or safety or any life threatening problem or death caused by or associated with a device, if that effect, problem, or death was not previously identified in nature, severity, degree of incidence. Additionally, an unanticipated adverse device effect includes any other unanticipated serious problem associated with a device that relates to the rights, safety, or welfare of subjects.

Severity of an AE is a clinical determination of the event intensity. The severity assessment for a clinical AE should be completed using the following definitions as guidelines:

Mild (+1): Awareness of sign or symptom, but easily tolerated.

Moderate (+2): Discomfort enough to cause interference with usual activity.

Severe (+3): Incapacitating with inability to work or do usual activity.

NOTE: An event that is fatal should be recorded as death on the **ADVERSE EVENT** eCRF. The cause of death will be detailed on the **Serious Adverse Events** section of the form.

A relationship to device or procedure of an AE is a judgment determination made by the PI that there is a logical connection between device use (e.g., delivery system manipulation) and the

occurrence of the AE.

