6.3 (15)	Updated Additional Evaluations. Revised Secondary endovascular procedure within 30 days, at 6 months, and annually to 5 years for resolution of endoleak Type I and II. Reason: to identify the procedure and resolution of endoleak Type I and III
4.2 (11)	Updated Background to include ePTFE covered stent. Reason: To reflect the Instructions for Use
8.6 (23)	Updated Protocol Deviation Reason: to clearly define a protocol deviation
8.7.1 (24)	Updated Serious Adverse Event Definition Reason: For alignment with ISO 14155 definition.
8.7.3 (26)	Added reference to Social Security Death Index (SSD) and CDC National Death Index (NDI) to obtain patient death information. Reason: Added additional information for sites to acquire patient death information
(43)	Updated monitoring will be performed under the direction of [name], Director, Clinical Affairs Reason: A new CRO will be contracted.
Attachment 2 (2)	Revised Informed Consent section 3. Up to 180 patients will be enrolled in the study overall. Reason: To reflect the change in the protocol.

Confidential. This document and the information contained herein may not be reproduced, used or disclosed without written permission from Endologix, Inc.

Section (Page)	Change and Reason for the Change
Attachment 2 (3)	Revised Informed Consent section 4. The US sites will be conducted under an IDE, or Canada under an investigational test authorization.
Attachment 3	Formatting changed to DD/MMM/YY throughout all Case Report Forms Reason: To correct formatting
Attachment 3 (1)	Revised Screening and Baseline case report form inclusion criteria section 3. Patient aneurysm increase of 1.0cm. Reason: to reflect the IFU
Attachment 3 (1)	Revised Screening and Baseline case report form inclusion criteria to include in section 4. Most caudal renal artery to aortoiliac bifurcation length \geq 70 mm Reason: to reflect the current IFU

Revision 03 changes

Note: minor punctuation or formatting changes are not included in this table.

Section (Page)	Change and Reason for the Change
All Pages	Changed all pages to protocol version from 02 to version 03, Date 09 Dec 2012 to 12 June 2013. Reason: Reflected revision date change in the header.
Table of Contents	Updated to reflect revision changes
1 (13)	‘Global’ changed to ‘regional’ Reason: PIs follow regional regulations. Protocol requirements will specify any non-regional requirements.

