8.2 (38)	‘global standards’ changed to ‘Good Clinical Practices’ Reason: Clarity
8.3 (27)	Changed title of Section 8.3 to properly reflect subsequent content Reason: Error, and as noted in FDA question #49.
8.3 (27)	Removal of methodology for patient naming. Reason: Patient IDs will be automatically generated within the eDC system.
8.5.4 (40)	Addition of sentence “If, during the index procedure, the device is not implanted and/or there is conversion to open surgery, the patient will be followed until the 30 day follow-up” Reason: Clarification of follow-up process for patients that either do not receive the study device, or are converted to open surgery.
8.7.1 (46)	‘...administered a product...’ changed to ‘...enrolled in the trial...’ Reason: Correction. AE reporting also applies to subjects who did not receive the product, but were enrolled.
8.7.2 (46) 8.7.3 (46)	Sections rewrite Reason: Consolidation. Many paragraphs in these two sections contained repetitious instructions. The adverse event reporting process is roughly the same regardless of the type of adverse event. AE reporting time requirements (from the site to Endologix), while mentioned, were scattered throughout text and difficult to access quickly. A table of “Adverse Events: required reporting timeframes” was generated to address this. Requirements for reporting and investigating a subject death were consolidated into one section. There were no substantive changes.
8.7.4 (46)	Removal of word ‘endovascular’ from section title Reason: Correction. Procedures discussed also refer to open repair.
8.7.4 (46)	Removal of fax information. Reason: reporting in this trial will be electronic via EDC.
8.7.6 (46)	Addition of Endologix reporting timeframes of UADEs. Removal of fax information Reason: Reporting will be done by the EDC system in this trial. Clarify Endologix response to such an event.
8.7.7 (46) 10.8 (60)	Revised definition for Clinically Significant Migration: Reason: Updated for consistency within the document.
8.7.7 (46)	Removal of definitions of various adverse events Reason: Consolidation. Definitions in the protocol will be limited to endpoints and device specific issues. All other clinical events will be defined by the independent CEC (Syntactx)

Section (Page)	Change and Reason for the Change

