8.8.4. Secondary procedures

For subjects that experience any non-diagnostic invasive secondary treatment of the groin access

Confidential. This document and the information contained herein may not be reproduced, used or disclosed without written permission from Endologix, Inc.

areas or of the abdominal aortoiliac vessels (e.g., hematoma drainage, vascular exploration for bleeding, iliac stenting, thrombectomy, additional device placement for endoleak, embolization for Type II endoleak, conversion to open repair, etc.), it is important to identify the specific procedure performed on the relevant **ADVERSE EVENT** eCRF. A copy of the discharge summary source document should be uploaded to the EDC system.

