8.8.7. Adverse Event Definitions

The following event definitions will be applied during this study.

- *Death:* Any death occurring during the study period, regardless of cause.
 - *Aneurysm-related death* is defined as any death occurring within 30 days from the date of the procedure, regardless of cause, and death due to aneurysm rupture or following any procedure intended to treat the aneurysm.
 - *Cardiac-related death* is defined as death due to arrhythmia, heart failure (including cardiogenic shock), or myocardial infarction.
 - *Pulmonary-related death* is defined as death due to pulmonary edema, respiratory failure, or pulmonary embolism.
 - *Vascular-related death* is defined as death due to stroke, cerebral hemorrhage, or other clear vascular event that is not categorized as cardiac-related or pulmonary-related.
 - *Other* is to be used to identify a death due to any event that cannot be clearly categorized as above, but where some information is available.
 - *Unknown* is to be used to identify a death where no information is available.
- *Procedural Technical Failure* is defined as a failure of the Nellix system to be delivered and deployed, such that the procedure is not completed, or the device failure results in a serious complication, or a residual endoleak occurs that cannot be resolved during the index procedure and is still present at the 30 day CT as read by the Core Lab.
- *Major Adverse Event:* An event occurring during the study that meets one of the following criteria:
 - *All-Cause Death* (see above);
 - *Bowel Ischemia:* the lack of adequate blood flow to the intestines that requires intensification of medical therapy or surgical/endovascular intervention;

- *Myocardial Infarction*: the presence of raised levels of one or more cardiac biomarkers in comparison to local laboratory reference ranges;
- *Paraplegia*: Paralysis of the lower extremities inclusive of the lower trunk;
- *Renal Failure*: the need for temporary or permanent dialysis or $>0.5\text{mg/dL}$ increase in pre-operative serum creatinine level at two consecutive intervals;
- *Respiratory Failure*: pneumonia or respiratory failure requiring ventilator support beyond 24 hours post-procedure;
- *Stroke*: a sudden development of neurological deficit due to vascular lesions of the brain such as hemorrhage, embolism, or thrombosis that persists for >24 hours;

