10.8 ADDITIONAL EVALUATIONS

- *Procedural and In-Hospital Evaluations:* The estimated blood loss volume, % of subjects receiving a blood transfusion, contrast volume, fluoroscopy time, endovascular device time, Polymer volume used, procedure time, anesthesia time and type, frequency of concomitant procedures, ICU time, time to hospital discharge, and % of subjects discharged to skilled nursing facilities or assisted living facilities who were not prior residents will be presented descriptively. Qualitative variables will be presented with rate. Quantitative variables will be presented with mean, standard deviation, median, minimum and maximum.
- *Mortality:* The proportion of subjects with mortality (all-cause and aneurysm-related) will be presented at 30 days and at each subsequent time point for which data are available (i.e., six months, and annually at years 1 through 5). A descriptive analysis and a Kaplan-Meier analysis of all-cause and aneurysm-related mortality through 30 days and for late follow-up including 30 days will be presented.
- *Major Adverse Events (MAE) Individual Components:* The proportion of subjects experiencing each category of MAE within 30 days and after 30 days at each subsequent time point for which data are available will be presented.
- *Composite Late MAEs (after 30 days):* The proportion of subjects experiencing an MAE after 30 days will be presented at each subsequent time point for which data are available. A descriptive analysis and a Kaplan-Meier analysis of the MAE composite will be

presented for follow-up through 30 days and for late follow-up including 30 days. The descriptive analysis will present the rates for the composite MAE and each individual adverse event that is part of the composite.

- *Aneurysm Rupture*: The proportion of subjects experiencing a rupture of the aneurysm will be presented at 30 days and at each subsequent time point for which data are available.
- *Conversion to Open Repair*: The proportion of subjects undergoing surgical conversion to open repair will be presented at 30 days and at each subsequent time point for which data are available.
- *Serious Adverse Events (SAEs)*: The proportion of subjects experiencing an SAE will be presented descriptively by time point.
- *Non-serious AEs*: The proportion of subjects experiencing a non-serious AE will be presented descriptively by time point.

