11. ADMINISTRATIVE PROCEDURES

11.1 STATEMENT OF COMPLIANCE

This clinical investigation will follow the international standard for Clinical Investigation of Medical Devices for Human Subjects -- Good Clinical Practice (ISO 14155:2011). The Sponsor and Investigator(s) will comply with their responsibilities as defined in 21 CFR 812.

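### The prevention-of-impairment criterion for a serious adverse event in 8.8.1 is limited to endovascular procedures, leaving a narrow gap for other treatment that neither needs nor prolongs a hospital stay

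*Combined protocol and SAP*

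**What the plan says.** Section 8.8.1 defines an SAE by alternative criteria. The first is death. The second is a serious deterioration in health that was life-threatening, caused permanent impairment, or "Required in-patient hospitalization or prolongation of existing hospitalization". The third, at issue here, is "Resulted in medical or surgical endovascular procedure to prevent permanent impairment to a body structure or a body function". The last concerns fetal harm. No other section restates or widens the definition.

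Other sections treat the kinds of treatment differently:

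- Section 8.8.7 defines bowel ischemia as a condition that "requires intensification of medical therapy or surgical/endovascular intervention", so medical, surgical and endovascular treatment are named separately.
- Section 8.8.7 also defines a secondary procedure as a non-diagnostic intervention for listed device problems, with no limit to endovascular methods.
- Section 8.8.4 asks sites to identify invasive re-treatment on the adverse event form. Its examples include "hematoma drainage, vascular exploration for bleeding, iliac stenting, thrombectomy" and conversion to open repair, and several of these need not be endovascular.

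Seriousness is used in three places. Section 8.8.3 sets site reporting times by it. Section 8.8.2 requires an extra part of the form for SAEs. Section 10.8 tabulates it: "The proportion of subjects experiencing an SAE will be presented descriptively by time point", with non-serious events shown in the same way.

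**The concern.** A medical treatment is not an endovascular procedure, so the phrase does not work as written, and a general word such as 'intervention' appears to have been meant. Read literally, an investigator may class as non-serious an event in which permanent harm was prevented by an open operation or by drugs, because nothing endovascular was done.

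This criterion exists for harm that was averted. The permanent-impairment criterion cannot stand in for it, because by assumption no permanent impairment occurred. The life-threatening and hospitalization criteria can stand in, but both sit under the condition of a serious deterioration in health. An event that was treated as an outpatient, or during the index stay without lengthening it, and that was not life-threatening may meet none of them.

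What is at stake is how fast sites report such an event, which descriptive table it enters, and the 10.8 determinations of whether a device-performance or implant-integrity finding was associated with an SAE.

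**Working it through.** The plan gives no figure to reproduce. The check is a reading of the criterion and of what else could catch the same events.

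**Step 1: the two ways to parse the phrase in 8.8.1.**

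| Treatment that averts permanent impairment | 'Medical or surgical' both qualify 'endovascular procedure' | 'Medical procedure', or 'surgical endovascular procedure' |
|---|---|---|
| Endovascular surgery | meets it | meets it |
| Open surgery | does not | does not (not endovascular) |
| Drug treatment | does not | does not (not a procedure) |
| Non-endovascular medical procedure | does not | meets it |

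Only the last row depends on the parse. Open surgery and drug treatment fall outside on both.

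**Step 2: choice or slip.** The 8.8.7 definitions of bowel ischemia and secondary procedure both use 'intervention' and do not confine it to endovascular methods. The change log, taken only as context, points the same way. Under Revision 03 the word 'endovascular' was taken out of the title of the secondary procedures section, on the ground that "Procedures discussed also refer to open repair". Under Revision 02 the SAE definition was updated: "Reason: For alignment with ISO 14155 definition". Section 11.1 states: "This clinical investigation will follow the international standard for Clinical Investigation of Medical Devices for Human Subjects". The standard's own text is not in the documents, and nothing here rests on it.

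**Step 3: what the other criteria catch.** Open surgery will usually need or prolong a hospital stay, and so will much of the medical treatment given for grave events. Others will be life-threatening. An event falls through only if all of these hold:

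1. the treatment averted permanent impairment;
2. it was not endovascular;
3. the event was neither fatal nor life-threatening;
4. no hospital stay was needed or prolonged.

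**Step 4: what changes for such an event (8.8.3 and 10.8).**

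| | If serious | If non-serious |
|---|---|---|
| Device- or procedure-related | 1 working day | 10 working days |
| Not related | 10 working days | monthly at minimum |
| Table in 10.8 | SAE | non-serious AE |

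The heading of 8.8.3 calls these times required, while its table column calls them recommendations. IRB/EC reporting rules apply in addition.

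**Step 5: effect on the SAE proportion.** Section 10.8 counts subjects, not events. A reclassified event changes the proportion only if that subject has no other SAE at that time point. One such subject is worth:

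- Pivotal Cohort at its maximum of 150: 1/150 = 0.67 percentage points;
- Pivotal Cohort at the 132 planned for one year: 1/132 = 0.76 points;
- Continued Access at its maximum of 250: 1/250 = 0.40 points;
- Roll-in at its maximum of 30: 1/30 = 3.3 points.

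The cohorts are evaluated separately, so these figures do not add. The documents give no basis for how many subjects would be affected.

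**Step 6: the primary endpoints.** The 30-day major adverse event composite uses component definitions in 8.8.7 that do not refer to this criterion. Treatment Success draws on two definitions that mention a serious complication (procedural technical failure and clinically significant migration), but the text does not link that term to the SAE definition. Both hypothesis tests stand apart from this point.

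**The case against.** The strongest case against is that little is lost. The criteria are alternatives, and open surgery, the most obvious example, will usually qualify through hospitalization. Events that do slip through are still recorded and reviewed:

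- 8.8.4 asks for invasive re-treatment of the groin or aortoiliac vessels to be identified on the adverse event form whether or not it is serious.
- 8.8.2 has the sponsor investigate every device- or procedure-related event.
- 11.2 provides an independent clinical safety review of all adverse events.
- Unanticipated device effects have their own wording in 8.8.1 and a 24-hour limit in 8.8.6.
- 10.8 tabulates non-serious events, so a reclassified event changes table and does not vanish.

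If the intended meaning is obvious, sites may also have applied it that way, and no document shows a site reading the phrase literally. Nor do the documents say that a haematoma drainage, for example, is done to prevent permanent impairment.

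Most of this stands and limits the size of the point. It does not repair the definition. The events committee in 11.2 categorizes events by the protocol's own definitions, so review does not clearly override the wording. The reporting time is also set by the site's classification before any review takes place.

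A reader might infer more: that open surgery is never an SAE in this study, that the primary safety result is understated, or that each missed event lowers the SAE rate by 0.67 points. The documents support none of these. The other criteria capture most open surgery, the composite has separate definitions, and the table counts subjects, so a missed event in a subject with another SAE at that time point changes nothing.

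**Conclusion.** The criterion is wrong as written and should be corrected. The gap is confined to non-endovascular treatment that averts permanent impairment without needing or prolonging a hospital stay, in an event that is not life-threatening. For each such event, the recommended site report moves from 1 to 10 working days if related, or from 10 working days to monthly if not, and the entry moves between two descriptive tables. No hypothesis test is affected.

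Two assumptions carry the conclusion. Sites and reviewers must apply the words literally, which the documents neither show nor rule out. Events of this kind must also occur, and their number cannot be derived. The percentage-point figures are therefore the weight of one subject with no other SAE at that time point, not an estimate of bias.

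**What to change.** In 8.8.1, replace 'endovascular procedure' with 'intervention' in this criterion and leave the rest of the sentence as it is. This matches the usage in 8.8.7.

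The edit alone is not enough. Section 8.6 shows that two-year data from the US trial had been reported to FDA by October 2016, and under 5.2 Continued Access opens only after primary enrollment closes. The index stays of the Pivotal Cohort are therefore past. Changing the wording only for future events would put two SAE definitions into one cohort's tables. The corrected criterion should also be applied to adverse events already recorded as non-serious, in each cohort, so that one definition is used throughout its tables.

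The cost is one phrase in the protocol, a limited re-review of recorded non-serious events, and a few more events classed as serious. Treatment, endpoints and sample size do not change.
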